4.2.2 Computing Environment

All statistical analyses will be performed using SAS statistical software (Version 9.4). Medical history and adverse events (AEs) will be coded using the latest available version of Medical Dictionary for Regulatory Activities (MedDRA). Concomitant medications will be coded using the latest available version of World Health Organization Drug Dictionary (WHO-DD).

4.2.3 Methods of Pooling Data

In the case of sparse data for the stratification factor (use of prophylactic medication: yes or no), the responses will be pooled in summary tables. Specific details on the procedures for pooling data are presented in the applicable sections of the document outlining the analyses.

4.2.4 Adjustments for Covariates and Stratification

The randomization of subjects is stratified by the use of prophylactic migraine medication (yes or no). Hence, most analyses are stratified by the use or prophylactic medication.

4.2.5 Multiple Comparisons

Type I error is controlled in this study by using a hierarchical gate-keeping procedure. First, the family of two co-primary endpoints is tested. If the co-primary endpoints are both found to be significant, then secondary endpoints are tested in a fixed sequence. In particular, each co-primary endpoint will be tested for superiority to placebo at a two-sided alpha level of 0.05 without further adjustment for multiplicity. If the primary endpoint tests are both significant, then the following secondary endpoints will be tested in a fixed sequence, in the order shown, with each test conducted at $p=0.05$:

1. Pain Relief at 2 hours
2. Functional Disability at 2 hours
3. Sustained Pain Relief from 2 to 24 hours
4. Sustained Freedom from MBS from 2 to 24 hours
5. Probability of Rescue Medication within 24 hours
6. Sustained Normal Functioning (on FDS) from 2 to 24 hours
7. Sustained Pain Relief from 2 to 48 hours
8. Sustained Freedom from MBS from 2 to 48 hours
9. Sustained Normal Functioning (on FDS) from 2 to 48 hours
10. Freedom from Photophobia at 2 hours

11. Functional Disability at 90 minutes
12. Pain Relief at 90 minutes
13. Sustained Pain Freedom from 2 to 24 hours
14. MBS Freedom at 90 minutes
15. Pain Freedom at 90 minutes
16. Freedom from Phonophobia at 2 hours
17. Sustained Pain Freedom from 2 to 48 hours
18. Pain Relief at 60 minutes
19. Functional Disability at 60 minutes
20. Freedom from Nausea at 2 hours
21. Pain Relapse from 2 to 48 hours

If a test in the hierarchy is not significant, then any further tests on endpoints in the sequence will have p-values presented only for descriptive purposes, and no conclusions will be drawn from those results.

For exploratory endpoints, no attempt will be made to adjust for multiplicity. Any exploratory endpoints for which p-values are produced will be evaluated at an unadjusted two-sided alpha level of 0.05 and presented only for descriptive purposes.

4.2.6 Subpopulations

The subgroups of interest for this study:

Age: Categorized as < 40 , ≥ 40 years

Race: white, black or African American, other (including Asian) , Asian only. Certain tables may be created for the Asian population only; but in the subgroup analyses, Asian subjects will generally be included in the “other” category due to low counts.

Sex: Female/Male

Aura: Presence/Absence

Headaches per Month: Categorized as $< \text{median}$, $\geq \text{median}$, where median is calculated overall across treatment groups combined for mITT subjects.

Triptan Non-Responder: Yes/No

Cardiovascular (CV) Risk Contraindicating Triptans: Yes/No

Subgroup analyses will be performed for the primary efficacy endpoints only.

Triptan non-responders are identified using the “Prior Triptan Response” Case Report Form (CRF) pages, which capture reasons for discontinuing triptans taken historically. The definition of triptan non-responder is based on the number of triptans that a subject failed for efficacy reasons. For each triptan and route of administration, the subject is asked the questions shown in Table 5. A subject is considered to have failed a drug for efficacy reasons if they indicated “most or all of the time” for any of the reasons in the table.

A triptan non-responder is defined as any subject that fails two or more molecular entities for efficacy reasons. To be considered a failure for a molecular entity, the subject must have failed on all routes of administration that the subject tried for the molecular entity.

Table 5: Questions Used to Determine Triptan Non-response

	Most or All of the Time	Some of the Time	Rarely	Never
The treatment took too long to relieve my headache pain.				
The pain returned after it was relieved within 24 hours				
The treatment did not relieve my other symptoms (nausea, sensitivity to light or sound, for example).				
I could not count on this treatment to relieve my pain and symptoms every time				

Subjects with CV risk that contraindicates triptans are identified using the “Cardiac and Other Risk Factors” CRF pages. The pages are used to identify subjects with cardiovascular conditions cited in triptan labels as contraindications. A subject is identified as someone with cardiovascular risk factors contraindicating triptans if any of the following questions are answered as “yes”:

Does the subject have ischemic coronary artery disease?

Does the subject have coronary artery vasospasm including Prinzmetal’s angina?

Does the subject have Wolff-Parkinson-White Syndrome or arrhythmias associated with other cardiac accessory conduction pathway disorders?

Does the subject have history of stroke or transient ischemic attack (TIA)?

Does the subject have peripheral vascular disease (PVD)?

Does the subject have ischemic bowel disease?

Does the subject have uncontrolled hypertension?

4.2.7 Missing and Partial Dates

For efficacy analyses, partial or missing dates will not be imputed. The relative study days, where determined, will be calculated for full dates only.

For rescue medication, if the time of rescue medication is missing, then all endpoints on or after the date of rescue medication will be imputed as failures.

For missing and/or partial dates regarding non-study medications, a conservative approach will be taken. The medication will be assumed to be concomitant if it cannot be definitively shown that the medication was not taken after the period beginning 14 days prior to the taking of study medication.

If the start date of an AE is partially or completely missing, then the date will be compared as far as possible with the date of the randomization. The AE will be assumed to be on-study if it cannot be definitively shown that the AE did not occur or worsen during the post-randomization period (worst case approach).

The following general rules will be used:

If the start day is missing, but the start month and year are complete, an AE will only be excluded as being on-study if the start month/year is before the month/year of randomization or if the stop date is before randomization.

If the start day and month are missing, but the start year is complete, an AE will only be excluded as being on-study if start year is before the year of randomization or if the stop date is before randomization.

If the start date is completely missing, an AE will be considered on-study unless the stop date is before randomization.

4.2.8 Visit Windows

Windows for the timeframe around efficacy measurements (15, 30, 45, 60, 90 minutes, 2, 3, 4, 6, 8, 24, and 48 hours) will be automated and captured in the eDiary. Refer to [Table 6](#) for details on the evaluation intervals and [Appendix 2](#) for details on the schedule of assessments.

Table 6: Evaluation Intervals for Efficacy Analysis

Evaluation	Protocol-Specified Interval	Analysis-Specified Interval
Screening Phase		
Screening	Day -28 to Day -3	Day -40 to Day -3
Acute (Randomization) Phase		
Baseline (Randomization)	Day 1	Day -2 to 1
Onset of Migraine	Day 1 to 45	Day 1 to 45
15, 30, 45, 60, 90 minutes post-dose	Time of Dose + 15, 30, 45, 60, and 90 minutes	Time of Dose + 15, 30, 45, 60, and 90 minutes (as captured in eDiary)
2 hours post-dose	Time of Dose + 2 hours	Time of Dose + 2 hours (as captured in eDiary)
3 hours post-dose	Time of Dose + 3 hours	Time of Dose + 3 hours (as captured in eDiary)
4 hours post-dose	Time of Dose + 4 hours	Time of Dose + 4 hours (as captured in eDiary)
6 hours post-dose	Time of Dose + 6 hours	Time of Dose + 6 hours (as captured in eDiary)
8 hours post-dose	Time of Dose + 8 hours	Time of Dose + 8 hours (as captured in eDiary)
24 hours post-dose	Time of Dose + 24 hours	Time of Dose + 24 hours (as captured in eDiary)
48 hours post-dose	Time of Dose + 48 hours	Time of Dose + 48 hours (as captured in eDiary)
End of Treatment Visit	Time of Dose + 7 days	> Day of Dose + 2 days (as defined by visit)

4.3 Planned Analyses

Study Day 1 is defined as the day of randomization. The analyses planned for endpoints that use data from this study only will be conducted after the last subject completes their End of Treatment Visit or discontinues from the study, and the database has been locked.

4.4 Subject Disposition

A summary of subject disposition will be tabulated for all enrolled subjects by treatment group and overall. The disposition table will support the creation of a consort diagram, similar to that shown in Figure 1. The categories in the table will include:

Number of subjects screened

Number of screened subjects excluded from the study and reason for exclusion

Number of subjects randomized

Number of subjects not treated, and the reasons for not being treated

Number of subjects treated, and their status

[figure not shown]
Completed Study

Discontinued, and reasons for discontinuation

Number of subjects in each analysis population

A by-subject listing of subject disposition information, including the reason for discontinuation, if applicable, will be presented.

Figure 2: Consort Diagram

4.5 Demographic and Baseline Characteristics

Demographic information, medical history by system organ class (SOC) and preferred term (PT), migraine history, cardiovascular risk factors, and prior/current triptan response will be summarized by as-randomized treatment group and overall for the mITT population to support efficacy. A similar set of tables will be made for the treated population by as-treated treatment group and overall to support safety.

A separate set of tabulations, including demographic information and migraine history, will be made for subjects enrolled but not randomized (overall only) and subjects randomized but not treated (by as-randomized treatment group and overall).

Demographic and other baseline data will also be provided in by-subject data listings.

For each subject, multiple medical histories of the same SOC or PT will be counted only once within each SOC and PT. Medical histories will be presented in descending order of overall frequency within SOC and PT.

4.6 Missing Efficacy Data Description

Descriptions and tabulations of missing data will only be concerned with the post-baseline time points required for computation of the primary and secondary endpoints, and will be assessed as-randomized. These include the time points measured from 2 hours through 48 hours post-dose (e.g.: 60 minutes, 90 minutes, 2, 3, 4, 6, 8, 24 and 48 hours). The other time points (15, 30, 45 minutes) are only required for the exploratory endpoints. Also, some tabulations focus on the pain endpoint as that should be generally descriptive of the other efficacy endpoints.

The number and percentage of (1) randomized subjects who do not meet the criteria for the mITT population, and (2) randomized and treated subjects who do not meet the criteria for the mITT population will be tabulated by treatment group and overall.

For the mITT population, the items below will be tabulated by treatment group and overall.

Number and percentage of subjects with missing pain data at each time point from 2 through 48 hours post-dose. The categories in this tabulation are not mutually exclusive as subjects may have missing data at multiple time points.

Number and percentage of subjects with: no missing pain data; 1 missing time point, 2 missing time points, 3 missing time points, 4 missing time points, 5 missing time points, 6 missing time points, or 7 missing time points. The categories in this tabulation are mutually exclusive.

The number and percentage of subjects with missing data on the following endpoints measured at 2-hours post-dose: pain, MBS, photophobia, phonophobia, nausea, and functional disability.

In addition, the number and percentage of mITT subjects with missing pain data at 2 hours post-dose will be displayed by treatment group and overall within the categories of each of the following subgroups:

Age: Categorized as < 40 or ≥ 40 years

Race: white; black or African American; other (including Asian); Asian only

Sex: Female or Male

Aura for study migraine: Presence or Absence

Headaches per Month: Categorized as < median or ≥ median (see Section 4.2.6)

Triptan Non-Responder: Yes/No

Rescue medication taken at any time during the study: Yes/No

MBS at migraine onset: photophobia, phonophobia, nausea, and not reported

4.7 Efficacy Evaluation

Unless otherwise noted, all efficacy analyses will be conducted using the mITT population as outlined below. Efficacy tabulations will present results by as-randomized treatment group only (excluding overall), unless specified otherwise. All efficacy data will be included in listings by subject, treatment group, and time point (as applicable).

For efficacy analyses, baseline is considered as the assessment at the onset of the treated migraine.

4.7.1 Rescue Medication

Subjects who take rescue medication will be considered as failures for any efficacy evaluations that are on or after the first rescue medication date/time. If the time of first rescue medication is missing, subjects will be considered as failures for any efficacy evaluations that are on or after the first rescue medication date.

Rescue medications are defined as non-study medications reported on the Rescue Medication CRF with complete medication dates, and either (1) medication date/time after the study drug first dose date/time, or (2) medication date equal to study drug first dose date if the medication time is missing.

The first rescue medication date/time is defined as the earliest rescue medication date/time, where missing time is considered to be earlier than non-missing time on the same date.

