Similarly, for treatment of non-qualifying migraines (i.e. mild migraines, or other headaches) that occur during the randomization period before a qualifying migraine is reported, subject will only be permitted to use the medications listed above. Triptans and acetaminophen (over 1000mg/day) are prohibited after randomization except as rescue medication as described in Section 5.4.1. In all circumstances, the subject will continue to complete his or her eDiary for up to forty-eight hours after consuming the study medication.

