5.4.1 Rescue Medications

After dosing with study medication, all other headache medication is prohibited during the 2 hours post dose. However, a subject who does not experience relief of their migraine headache at the end of two hours after dosing with study medication (***and after the two hour assessments have been completed on the eDiary***), will be permitted to use the following rescue medication: ***aspirin, ibuprofen, acetaminophen up to 1000mg/day (this includes Excedrin Migraine) naprosyn (or any other type of non-steroidal anti-inflammatory (NSAID)), antiemetics (e.g., metoclopramide or promethazine), or baclofen. These are the only medications allowed for rescue treatment after 2 hours post dose of study medication.***

However, if needed, after 48-hours of administering the one dose of study medication (and before coming in for the End of Treatment Visit) subject may take their prescribed standard of care medications for treatment of migraine (including triptans if not contraindicated, provided all of the assessments have been completed on the eDiary. Similarly, if the migraine is relieved by study medication at 2 hours after dosing but then recurs to a moderate or severe intensity level between two and forty-eight hours, the subject will be permitted to take the same rescue therapy as outlined above. In all circumstances, the subject will always continue to complete his or her eDiary entries through the 48-hour assessment after consuming the study medication. Use of concomitant medication after randomization, including rescue medication, will be recorded by the subject on a paper diary and reported to the site. The site will record medications that were taken within 14 days of dosing with study medication (or until the End of Treatment Visit).

During the 45 days the subject is participating in the study, if the subject has a nonqualifying migraine (mild migraine) or a migraine that they do not treat with study medication, the subject is permitted to use only the following medications: aspirin, ibuprofen, naprosyn (or any other type of non-steroidal anti-inflammatory (NSAID)), antiemetics (e.g., metoclopramide or promethazine), or baclofen.

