2.3 Study Estimands

The tables that follow lay out the estimands corresponding to the study objectives. In these tables, the following abbreviations are used to describe the handling of intercurrent events for efficacy estimands:

NC=F: Non-Completers = Failure.

A subject with any missing data for an endpoint is classified as a treatment failure.

NC1=F: Non-Completers with more than 1 missing data point = Failure.

Subjects with more than 1 missing data point, other than at the 2, 24 or 48 hour data points, are classified as treatment failures. This applies to endpoints that are based on data from multiple time points. For example, for the durability endpoint of sustained pain freedom from 2 to 24 hours, the subjects should provide data at 2, 3, 4, 6, 8, and 24 hours. For NC1=F imputation, the data at 2 and 24 hour time points must be present or the subject is classified as a failure. However, any single data point may be missing at 3, 4, 6 or 8 hours without penalty. For

sustained pain freedom from 2 to 48 hours, the data at 2, 24, and 48 hours are required to be present.

RM=F: Rescue Medication = Failure.

Subjects that take rescue medication before, or at, the time of the event of interest are classified as failures. If the time of rescue medication is missing, all events on or after the date of rescue medication are classified as failures.

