2.3.1 Primary Estimands

The estimands corresponding to the co-primary objectives for this study are shown in [Table 1](#).

The population summary for all primary estimands is the difference in the percentage of subjects with a positive result (‘risk difference’) between the BHV-3000 and the Placebo treatment groups. This summary is computed using the modified Intent-to-Treat (mITT) population as defined in section 3.1.

Table 1: Estimands for the Co-Primary Objectives

Objective	Pain Freedom at 2 hours post-dose
Population	mITT
Variable	Percent of subjects reporting no pain at 2 hours post-dose
Intercurrent Events	NC=F; RM=F.
Objective	Freedom from Most Bothersome Symptom (MBS)
Population	mITT
Variable	Percent of subjects reporting absence of their MBS at 2 hours post dose
Intercurrent Events	NC=F; RM=F; Failure to report MBS = F; Study medication taken before reporting MBS=F.

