3.2 Protocol Deviations

A protocol deviation is any variance from the approved protocol, either intentional or unintentional. The possible categories for all protocol deviations are as follows:

- Informed Consent
- Inclusion/Exclusion Criteria (specify #)
- Concomitant Medication
- Serious Adverse Event (SAE) Reporting
- Regulatory
- Drug Storage/Preparation
- Drug Administration
- Visit Schedule
- EPro Diary Noncompliance
- Noncompliance (i.e., trends, missed assessments).

A significant protocol deviation is any deviation that could impact subject safety or the integrity of the trial. For the purposes of this study, significant protocol deviations will be defined as the following:

- Inadequate informed consent or initiation of study procedures prior to completing the informed consent
- Enrollment of subjects not meeting the inclusion/exclusion criteria
- Unreported SAEs
- Improper breaking of the blinding of the study
- Use of prohibited medication as defined by the protocol
- eDiary non-compliance with primary and secondary endpoints (2, 24, or 48-hour post-dose assessment)
- Repeated deviations of the same nature for a given site or subject
- Initiation of rescue medication(s) prior to primary endpoint at 2-hours

The sponsor, or designee, will be responsible for producing the final protocol deviation file (formatted as a Microsoft Excel file). This file will include site, subject ID, deviation date, deviation type, and a description of the protocol deviation.

All protocol deviations (with the exception of those related to rescue medication and missed eDiary assessments) will be presented in a by-subject listing. Handling of rescue medication and missed eDiary assessments are described in the statistical methods section of this SAP.

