4.9.6 Non-Study Medications

Concomitant medications will be coded using the WHO-DD. Results will be tabulated by Anatomic Therapeutic Class (ATC) and PT in descending order of overall frequency. For each subject, multiple records of the same medication will be counted only once within each ATC and/or PT.

The following non-study medications will be tabulated:

- Prior medications, defined as non-study medications with start or stop date < randomization date – 14 days.
- Concomitant medications, defined as non-study medications with start or stop date ≥ randomization date – 14 days.
- Prophylactic medications taken at or after informed consent and before randomization, defined as those with (1) informed consent date ≤ start or stop date < randomization date, or (2) start date ≤ informed consent date and randomization date – 1 day ≤ stop date

- Prophylactic medications taken at or after randomization, defined as those with start or stop date \geq randomization date.
- Rescue medications (see Section 4.7.1).

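### SAP 4.7.1 identifies rescue medication by CRF page, so a prohibited acute drug recorded as concomitant is not scored as a failure; the exposure is mainly on the sustained, relapse and rescue-use endpoints

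*SAP*

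**What the plan says.** **The failure rule.** SAP 2.3 states: "Subjects that take rescue medication before, or at, the time of the event of interest are classified as failures". Table 1 applies RM=F to both co-primaries; for the most bothersome symptom (MBS) the intercurrent events are "NC=F; RM=F; Failure to report MBS = F; Study medication taken before reporting MBS=F". Table 2 applies it to 20 of the 21 secondaries. The exception is secondary endpoint 5, rescue use within 24 hours, where rescue is itself the variable.

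**The definition.** SAP 4.7.1: "Rescue medications are defined as non-study medications reported on the Rescue Medication CRF with complete medication dates". The entry must also be timed after study drug, or dated the same day if its time is missing. There is no drug list, and no other CRF page is named.

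**Other drugs.** SAP 4.9.6 has a separate category: "Concomitant medications, defined as non-study medications with start or stop date" on or after a cut-off 14 days before randomization. It is tabulated and has no link to efficacy failure. SAP 3.2 lists "Use of prohibited medication as defined by the protocol" as a significant deviation, separately from rescue started before the 2-hour endpoint.

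**The protocol.** Section 5.4.1 names the permitted rescue drugs and adds: "These are the only medications allowed for rescue treatment after 2 hours post dose of study medication". Standard-of-care drugs, including triptans, are allowed only after 48 hours. Section 4.3.2 says: "Triptans and acetaminophen (over 1000mg/day) are prohibited after randomization except as rescue medication as described in Section 5.4.1". The source record is shared: "Use of concomitant medication after randomization, including rescue medication, will be recorded by the subject on a paper diary and reported to the site".

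**The concern.** RM=F exists so that a response helped by another acute treatment is not counted as a response to study drug. A definition tied to a CRF page does this only if every acute drug taken for the attack reaches that page. The documents do not settle whether a prohibited one would.

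Read as a closed list, Protocol 5.4.1 suggests that a triptan at 12 hours is not rescue but a prohibited concomitant drug and a deviation. Yet Protocol 4.3.2.1 and the synopsis describe opioids, ergotamines and butalbital compounds as a kind of rescue medication that is excluded, and 4.3.2 speaks of triptans as rescue. Two careful sites could file the same drug differently, and the SAP would score one subject a failure and the other a success.

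The sustained endpoints are the most exposed. The diary has no rating between 8 and 24 hours or between 24 and 48 hours, so a recurrence treated in those gaps may show only in the medication record. The endpoints concerned are numbers 3, 4, 6 to 9, 13 and 17 in the fixed sequence, plus relapse (21) and rescue use (5). In such a sequence, one changed result decides whether later endpoints can be claimed.

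**Working it through.** **1. Does any other rule catch the drug?**

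- Population: mITT (SAP 3.1) requires randomization, dosing, a moderate or severe migraine and one post-baseline value. It keeps users of prohibited drugs. SAP 3.1 defines no per-protocol set.
- Deviations: use of prohibited medication goes to a by-subject listing (SAP 3.2). Nothing is excluded or imputed.
- Sensitivity analyses (SAP 4.7.3.1, 4.7.3.2 and the revision history): LOCF, complete cases, multiple imputation, varied success rates, an MBS stratum, and exclusion of Site 002. None treats non-rescue acute drugs as failure.

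So no other rule catches it.

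**2. The same behaviour on two pages**

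| Subject | On the Rescue CRF | On the concomitant page only |
|---|---|---|
| Triptan at 12 h for the treated attack; pain rated none at 2, 3, 4, 6, 8 and 24 h | Sustained pain freedom 2–24 h: failure. Rescue within 24 h: yes | Sustained pain freedom 2–24 h: success. Rescue within 24 h: no |
| Triptan at 1 h; pain rated none at 2 h | Co-primary pain freedom: failure | Co-primary pain freedom: success |

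The second row needs a drug taken by the 2-hour assessment; the first does not.

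**3. The plan's own figures**

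Treated per arm: 0.85 × 715 = 607.75, stated as about 600. Joint power: 0.95² = 0.9025, stated as roughly 90%. Both reproduce, and this point disputes neither. The 95% per endpoint cannot be reproduced because the response rates behind it are not stated.

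**4. Illustrative size (assumed counts)**

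Suppose 0.5 to 2% of 600 per arm are misclassified: 0.005 × 600 = 3 to 0.02 × 600 = 12. These must be subjects who took such a drug, had it recorded off the Rescue page, and otherwise met the endpoint. If the misclassified fractions are f_A (active) and f_P (placebo), the risk difference moves by f_A − f_P.

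The smallest significant difference d, with p₁ = p₀ + d, solves d = 1.96 × √{[p₀(1 − p₀) + p₁(1 − p₁)]/600}.

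- p₀ = 7.4% (Phase 2b placebo, sustained pain freedom 2–24 h, Protocol 1.3.2): 1.96 × √[(0.0685 + 0.0948)/600] ≈ 3.2 points, about 19 subjects.
- p₀ = 15%: 1.96 × √[(0.1275 + 0.1558)/600] ≈ 4.3 points, about 26 subjects.

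An imbalance of 6 subjects is 6/600 = 1 point.

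For power, assume placebo success of 15.3% (Phase 2b pain freedom at 2 h) and the difference that gives 95% power at 600 per arm, 8.2 points. Power = Φ[(d − 1.96·se₀)/se₁], with se₀ the pooled and se₁ the unpooled standard error.

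| Extra successes, placebo/active | Observed difference | Power |
|---|---|---|
| 0/0 | 8.2 | 95% |
| 6/6 | 8.2 | 94.3% |
| 6/3 | 7.7 | 91.6% |
| 6/0 | 7.2 | 88.0% |
| 12/6 | 7.2 | 86.8% |
| 3/6 | 8.7 | 96.5% |

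Example, 12/6: rates 17.3% and 24.5%, se₀ = 0.02348, se₁ = 0.02338; (0.0721 − 0.0460)/0.02338 = 1.12, giving 86.8%.

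With no true effect, 6 extra successes in the active arm only raise two-sided rejection from 5% to 7.6% at a 15.3% placebo rate, or to 6.8% at 25%.

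**The case against.** The best defence is that the documents mostly use rescue to describe purpose. The protocol has permitted and excluded kinds, and SAP 3.2 treats use before 2 hours as rescue even though the timing is forbidden. SAP 4.7.1 covers any non-study drug on the rescue page, so a triptan entered there is a failure. The eCRF instructions and take-home medication logs (Protocol 6.1) are not in the documents and may send every post-dose acute drug to that page. Sites are blinded, so unequal recording between arms is not the natural expectation.

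Most of this stands. It limits how often the gap would open, but it does not close it: the SAP neither states nor cites such routing, and 4.7.1 is the rule a programmer will follow.

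Three stronger readings are tempting and not supported.

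- *The co-primary result is generally unsafe.* Only drugs taken by the 2-hour assessment matter there, and SAP 3.2 points towards treating those as rescue.
- *The error favours rimegepant.* The documents give no direction. More such use on placebo would make the analysis conservative.
- *Every analgesic, NSAID or antiemetic on the concomitant page should be a failure.* That would fail subjects treated for unrelated reasons and change what endpoint 5 measures. If the missing-time rule in 4.7.1 were carried over, it could also fail a subject whose drug was taken before study drug on the same day.

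**Conclusion.** The gap is in the text: under SAP 4.7.1 as written, a prohibited acute drug taken post-dose for the treated attack and recorded as concomitant does not trigger RM=F, and no other rule does. It should be closed, mainly for the sustained, relapse and rescue-use endpoints.

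Its size is unknown. Frequency, routing and direction are not given, and the 3 to 12 subjects per arm are an assumption. Within that range, equal misclassification costs little (95% to 94.3% power at 6/6). An imbalance of 6 subjects moves the difference by 1 point, against about 3.2 points needed for significance at a 7.4% placebo rate. That could decide a borderline step in the fixed sequence, but it is no ground for expecting a wrong primary conclusion.

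**What to change.** **In SAP 4.7.1**, count as RM=F any acute migraine or headache medication, permitted or prohibited, taken after study drug for the treated attack, whichever medication CRF page it is on.

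- Identify these by blinded review of WHO-DD coded terms, indication and timing before unblinding.
- Exclude stable prophylaxis, permitted low-dose aspirin and drugs taken for a clearly non-migraine reason.
- State in advance how a missing time or reason on the concomitant page is handled, and how an incomplete date is handled. As written, a Rescue CRF entry with an incomplete date is also not rescue.
- Use the same definition for secondary endpoint 5, relapse and the time-to-rescue analysis (SAP Appendix 3, section 2.1).
- Report the Rescue-CRF-only definition as a sensitivity analysis.

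The protocol passages on whether excluded drugs are rescue (4.3.2, 4.3.2.1 and 5.4.1) should be reconciled. This point takes no view on which drugs should be permitted.

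**Cost:** SAP wording and a small blinded review of medications already collected and coded. Some judgement is needed where the concomitant record lacks a time or reason, and response rates may fall slightly.
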